4.3.3 Sensitivity analysis

For the primary estimand for the primary endpoint, no sensitivity analysis will be performed. However, three supplementary analyses will be performed as described in the section below.

4.3.4 Supplementary analyses

The following supplementary analyses will be performed:

As-observed analysis (including all data after taking the prohibited and/or rescue medications)

The data collected after taking all prohibited medications and/or rescue medications will be included in the supplementary analysis to evaluate the robustness of the primary analysis results with respect to the method of handling data while taking the prohibited medications (eg, treatment policy strategy). In addition, for participants discontinuing the study treatment before Week 24, their off-study treatment values measured up to Week 24 will be included in the analysis. The participants having missing data at Week 24 regardless of reason(s) will be considered non-responders at that timepoint.

Hybrid method analysis (the worst-observation carried forward (WOCF) and multiple imputation (MI))

In the primary analysis of change from baseline in WI-NRS (continuous variable) at Week 24, the hybrid method of the WOCF and MI will be used (see [Section 4.4.2](#)). Similar to the continuous variable, the same imputation method will be used in the analysis of the proportion of participants with improvement (reduction) in WI-NRS by ≥ 4 from baseline to Week 24, which is consistent for the intercurrent event strategy and missing data handling in the binary variables and continuous variable. That is, after the imputation of continuous WI-NRS data at Week 24 using the hybrid method of the WOCF and MI (see [Section 4.4.2](#)), responders will be defined as patients with improvement in WI-NRS by ≥ 4 from baseline to Week 24 in each of the imputed datasets with about 40 imputations, and then the CMH test adjusted by documented history of atopy (atopic or non-atopic), stable use of TCS/TCI (yes or no), region, and baseline anti-depressant use (yes or no) will be used. Statistical inference obtained from all imputed data will be combined using Rubin's rule.

Tipping point analysis

The intercurrent events will be handled as follows:

- Discontinuation of study treatment before Week 24: Off-study treatment data up to Week 24 will be included in the analysis (treatment policy strategy).
- Taking the prohibited medications/procedures and/or rescue medications prior to Week 24: Data after the intercurrent events will be censored and then imputed with the below tipping point method

In addition, the missing data imputation rules are as follows:

- Having missing data at Week 24: Data will be imputed with the following tipping point method.

Tipping point method:

- A sequence of analyses will be performed with the adjustment to artificially decrease the response rate in the dupilumab group and increase the response rate in the placebo group with a fixed and definite set of values for data imputation.
- For each combination of increasing response rate in placebo and decreasing response rate in dupilumab, multiple imputed datasets will be generated and analyzed using CMH test. The results obtained from multiple imputed datasets will be combined to generate statistical inference, ie, p-value and treatment difference between 2 treatment groups.
- A “tipping point” will be identified while the result is no longer statistically significant (ie, p-value >0.05).

4.3.5 Subgroup analyses

To assess the homogeneity of the treatment effect across various subgroups, analyses will be performed on the primary endpoint across the following subgroups (categories with fewer than 5 participants may be combined with other categories):

- Age group (<65, \geq 65 years)
- Gender (Male, Female)
- Region
- Territory
- Race (Caucasian/White, Black/of African descent, Asian/Oriental, Others)
- Ethnicity (Hispanic or Latino, Not Hispanic or Latino)
- Baseline weight (<60, \geq 60- <90, \geq 90 kg)
- Baseline BMI (<25, \geq 25- <30, \geq 30 kg/m²)
- Participants without a current diagnosis of AD
- History of atopy (atopic or non-atopic)
- Stable use of TCS/TCI (yes or no)
- Antidepressant use (yes or no) at baseline
- Baseline IGA PN-S moderate versus severe (3 versus. 4)
- Participants who have not been impacted by COVID-19 vs impacted by COVID-19 (for participants who have been impacted by the COVID-19, the efficacy data will be descriptive only if the number of participants is not enough to perform statistical tests. Participants impacted by the COVID-19 pandemic are defined as randomized participants with any critical or major deviation related to COVID-19 or who permanently discontinued study intervention or study due to COVID-19.)

To test the interaction between intervention and subgroup factor, a logistic regression model incorporating subgroup-by-treatment interaction will be built for each subgroup factor except the

subgroup of participants without a current diagnosis of AD (very few AD participants will be excluded). The model will include all the covariates in the main statistical model plus the subgroup variable and the subgroup-by-treatment interaction. A p-value for the test of interaction will be provided.

In each subgroup, the treatment effects for the primary endpoint will be provided, as well as the corresponding 95% CI, using the same method as applied to the primary analysis. Forest plots will be provided.

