1.2.1 Estimands

The primary estimands defined for main endpoints are summarized in below [Table 3](#). More details are provided in [Section 4](#).

Table 3 - Summary of primary estimand for main endpoints

Endpoint Category	Estimands			
	Endpoint(s) ^a	Population	Intercurrent event(s) strategy and missing data handling	Population-level summary
Primary objective: To demonstrate the efficacy of dupilumab on itch response in participants with PN, inadequately controlled on topical prescription therapies or when those therapies are not advisable.				
Primary endpoint	Proportion of participants with improvement (reduction) in worst-itch numeric rating scale (WI NRS) by ≥ 4 from baseline to Week 24	ITT	
The intercurrent events will be handled as follows:
 
 Discontinuation of study treatment before Week 24: Off-study treatment data up to Week 24 will be included in the analysis (treatment policy strategy). Taking the prohibited medications/procedures and/or rescue medications^b prior to Week 24: Participants will be considered as non-responders (composite strategy). 
In addition, the missing data imputation rules are as follows:
 
 Having missing data at Week 24: Participants will be considered as non-responders 	CMH test adjusted by documented history of atopy (atopic or non-atopic), stable use of TCS/TCI (yes or no), region (countries combined), and baseline antidepressant use (yes or no).
Secondary objective: To demonstrate the efficacy of dupilumab on additional itch endpoints in participants with PN, inadequately controlled on topical prescription therapies or when those therapies are not advisable.				

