For any participant randomized more than once, only the data associated with the first randomization will be used in any analysis population. The safety experience associated with any later randomization will be reported separately.

For participants receiving more than one study intervention (placebo and dupilumab) during the study, the intervention group for as-treated analysis will be the dupilumab group.

Regarding the COVID-19 pandemic, additional summaries by COVID-19 subgroups (ie, impacted by the COVID-19 pandemic and NOT impacted by the COVID-19 pandemic) will be provided to assess the impact of COVID-19 on treatment effect. Participants impacted by the COVID-19 pandemic are defined as randomized participants with any critical or major deviation related to COVID-19 or who permanently discontinued study intervention or study due to COVID-19.

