4.3 PRIMARY ENDPOINT(S) ANALYSIS

4.3.1 Definition of endpoint(s)

The primary endpoint for this study is the proportion of participants with improvement (reduction) in worst-itch numeric rating scale (WI-NRS) by ≥ 4 from baseline to Week 24.

WI-NRS is a patient-reported outcome (PRO) comprised of a single item rated on a scale from 0 (“No itch”) to 10 (“Worst imaginable itch”). Participants are asked to rate the intensity of their worst pruritus (itch) over the past 24 hours using this scale.

The weekly average WI-NRS score at each week, which is defined as the average of daily non-missing scores within the week window of each week (see [Section 5.4](#)), will be used for analyses.

For efficacy analysis, [Table 5](#) presents the prohibited and rescue medications/procedures which will be considered as intercurrent events if the last column indicates as “Yes” and therefore be handled in the estimands for endpoints defined in [Table 3](#).

Table 5 - Prohibited medications/procedures and rescue medications that impact efficacy

Medication/procedure	Comment	Data to be set as non-responder after taking medication in the main statistical analysis (Yes/No) ^a /Selection criteria
Prohibited medications/procedures		
Systemic immunosuppressive/immunomodulating drugs (eg, systemic corticosteroids, cyclosporine, mycophenolate-mofetil, interferon gamma, Janus kinase inhibitors, azathioprine, methotrexate, hydroxychloroquine, dapsone, sulfasalazine, colchicine, etc)	IMP to be discontinued	Yes (CDG ^b Immunosuppressant drugs Narrow and SDG ^b Corticosteroids Narrow)
Other monoclonal antibodies (that are biological response modifiers).	IMP to be discontinued	Yes (SDG ^b SDGMonoclonal antibodies Narrow)
Phototherapy, including tanning beds.	IMP to be discontinued	Yes (CMQ ^b HLT Phototherapies, CMQ ^b Tanning_single PT)
Naltrexone or other opioid antagonist	IMP to be discontinued	Yes (SDG ^b Analgesia producing opioids NARROW)
Gabapentin, pregabalin, and thalidomide	IMP to be discontinued	Yes (CDG ^b Gabapentin mono and multi ingredients, Pregabalin mono and multi ingredients, or Thalidomide mono and multi ingredients)
Paroxetine, fluvoxamine or other SSRIs.	No IMP discontinuation, see requirement in the footnote	Yes ^{c,d} (CDG ^b N06AB selective serotonin reuptake inhibitors)
SNRIs.	No IMP discontinuation, see requirement in the footnote	Yes ^{c,d} (CDG ^b serotonin and norepinephrine reuptake inhibitors)

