4.3.2 Main analytical approach

The primary estimand for the primary endpoint is the treatment policy/composite approach as defined in [Table 3](#).

The primary analysis population for the efficacy endpoints will be the ITT population.

The following null hypothesis H0 and alternative hypothesis H1 will be tested for dupilumab against placebo:

- H0: No treatment difference between dupilumab and placebo.
- H1: There is a treatment difference between dupilumab and placebo

The primary analysis will be conducted by using Cochran–Mantel–Haenszel test (CMH) test adjusted by documented history of atopy (atopic or non-atopic), stable use of TCS/TCI (yes or no), region, and baseline anti-depressant use (yes or no). Comparisons of the response rates between dupilumab and placebo will be derived. In addition, odds ratio and response rate difference as well as the corresponding 95% confidence intervals (CI) will be provided along with the p-values.

As defined in [Table 3](#) for participants discontinuing the study treatment before Week 24, their off-study treatment values measured up to Week 24 will be included in the analysis. Participants taking the prohibited medications/procedures and/or rescue medications (see [Table 5](#)) prior to Week 24 or having missing data at Week 24 will be considered non-responders.

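### The COVID-19 subgroup is defined by post-randomisation events that partly determine the outcome, so its row estimates and interaction p-value cannot be read as effect modification

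*SAP*

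**What the plan says.** SAP 4.3.5 lists 14 subgroup factors. Thirteen are demographic or baseline characteristics. The last is COVID-19 impact, which a participant acquires through any critical or major "deviation related to COVID-19 or who permanently discontinued study intervention or study due to COVID-19". SAP 3 gives the same definition and offers "additional summaries by COVID-19 subgroups" as the way to judge what the pandemic did to the treatment effect. The SAP version history says a health authority asked for this.

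On testing, 4.3.5 states that "a logistic regression model incorporating subgroup-by-treatment interaction will be built for each subgroup factor" and that "A p-value for the test of interaction will be provided". The only exemption is the subgroup without a current AD diagnosis. If too few impacted participants are available for testing, their data are only described, but no threshold is given. SAP 4.4.1.2 repeats the subgroup analyses for the key secondary endpoints.

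On the outcome, SAP 4.3.2 provides that participants "having missing data at Week 24 will be considered non-responders". Stopping study treatment alone does not cause failure, because Table 3 keeps off-treatment values up to Week 24. The weekly itch score is the "average of daily non-missing scores within the week window of each week". For Week 24 the window is Days 166–172 for the diary (Table 10) and Days 127–210 for IGA PN-S (Table 11).

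Protocol 9.4.3 leaves to the SAP any methods needed for COVID-19's effect on efficacy, and gives missing data as an example.

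**The concern.** A subgroup analysis supports a statement about effect modification when membership is fixed before treatment starts, so that each row remains a randomised comparison. Here membership depends on what happened during the study. In addition, one membership event feeds straight into the endpoint: a COVID-19 exit before the Week 24 window places the participant in the impacted row and sets the response to failure. The other row is in turn cleared of those failures, while its own non-COVID dropouts still count as non-responders.

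The contrast between rows therefore mixes any real effect of the pandemic with the missing-data rule and with the pattern of exits by arm. The SAP carries no warning, and the p-value is the figure most likely to be quoted in answer to the authority's question.

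**Working it through.** **Plan figures.** The documents give no figure for the COVID-19 subgroup. The only sizing figure is 56 per arm for 90% power (Fisher exact, two-sided 0.05; SAP 2), with 75 per arm randomised. The response rates are redacted, so 56 cannot be confirmed. Rate pairs that give 90% power at 56 per arm are, placebo v dupilumab: 0.10 v 0.366, 0.15 v 0.437, 0.20 v 0.501, 0.25 v 0.564 and 0.30 v 0.620.

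**Assumptions for the base case.** True response is 20% v 45%, COVID-19 has no effect on the drug, and 12 of 150 are impacted (6 per arm). A share q of the impacted leaves before Week 24, and those who leave would have responded like the rest.

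**Formula.** In the impacted row the observed rate in each arm is p(1 − q).

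| q dupilumab | q placebo | Observed rates | Difference (points) | Odds ratio |
|---|---|---|---|---|
| 0 | 0 | 45% v 20% | 25 | 3.27 |
| 0.25 | 0.25 | 33.75% v 15% | 18.75 | 2.89 |
| 0.50 | 0.50 | 22.5% v 10% | 12.5 | 2.61 |
| 0.75 | 0.75 | 11.25% v 5% | 6.25 | 2.41 |
| 1/6 | 3/6 | 37.5% v 10% | 27.5 | 5.40 |

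The fourth row uses (0.1125/0.8875)/(0.05/0.95) = 2.41; the other odds ratios are formed the same way. The last row is one exit among six on dupilumab against three among six on placebo. Imbalance of that size reverses the direction on both scales.

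**Across the 90%-power pairs.** With equal q = 0.50, the difference halves and the odds ratio is multiplied by 0.82 (placebo 0.10) down to 0.67 (placebo 0.30). At 0.20 v 0.501 the odds ratio without exits is 4.02. With q = 0.10 on dupilumab, the impacted row shows a larger odds ratio once q on placebo exceeds 0.151. At q = 0.40 on placebo it is 6.02.

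**The other row also contains forced failures.** If the planned 15% dropout applied there, equally by arm, its difference would be 0.85 × 25 = 21.25 points. An impacted row with q = 0.25 (18.75) would then be only 2.5 points lower. One with q = 0.10 (0.90 × 25 = 22.5) would be higher.

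**What the interaction test can see.** In the base case with q = 0.50 and no forced failures in the other row:
- Log odds ratio shift: ln(2.61/3.27) = −0.23.
- Variance, impacted row: 1/(6 × 0.225 × 0.775) + 1/(6 × 0.10 × 0.90) = 0.956 + 1.852 = 2.808.
- Variance, other row: 1/(69 × 0.45 × 0.55) + 1/(69 × 0.20 × 0.80) = 0.149.
- Standard error: √2.957 = 1.72. Rejection probability is about 5%.
- Significance needs a log shift of 1.96 × 1.72 = 3.37, a ratio of odds ratios of about 29.
- The chance of no placebo responder in the impacted row is 0.90⁶ = 0.53, which leaves the logistic model with an empty cell.

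With 10% to 30% of 150 impacted, equal q of 0.25 to 0.75 and placebo rates of 0.10 to 0.25 (paired as above), rejection runs from 5.0% to 6.8%.

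**Effect on the primary result.** In the base case the ITT difference is (138 × 25 + 12 × 12.5)/150 = 24.0 points, against 25 with no forced failures.

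**The case against.** A reader might infer that the impacted row must show a smaller effect by construction. The documents do not support that. A deviation leaves observed data in use, and stopping treatment keeps off-treatment values. Leaving during the 12-week follow-up does not touch Week 24. The itch score comes from a daily diary, so a missed visit need not remove it. For IGA PN-S, an end-of-treatment or early-discontinuation assessment from Day 127 can serve as the Week 24 value. Attenuation requires exits that are similar by arm and more frequent than forced failures in the other row, and the SAP guarantees neither. It is also smaller on the odds ratio scale, where the test operates, than on the difference scale.

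Three further points count against the concern. First, the clause that makes small impacted groups descriptive would plausibly apply with 12 participants. It is conditional, has no threshold, and deals with precision rather than with how the group is defined, so it does not settle the matter. Combining categories with fewer than five participants does not help a two-level factor either.

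Second, the hybrid and tipping-point analyses in SAP 4.3.4 already replace missing-as-failure, including for COVID-19 exits, and 4.4.1.2 extends them to the key secondary endpoints. This stands, and it makes a further analysis optional. Neither isolates COVID-19, because both also change the handling of other missing data and of prohibited or rescue medication.

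Third, this is one of 14 factors, outside the testing hierarchy in SAP 4.6. That also stands and limits the weight of the point. Nothing in the documents shows that treatment influences who is impacted, but with six per arm chance alone can produce unequal exits.

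**Conclusion.** The point holds as one of interpretation. Membership is post-randomisation, and one route into the impacted group also sets the outcome. The row estimates and the interaction p-value therefore cannot answer the question that SAP 3 poses. The bias in the impacted row is towards a smaller effect if COVID-19 exits before Week 24 are similar by arm and outnumber forced failures in the other row. Otherwise it can go either way.

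The size depends on assumed response rates, impacted share and exit shares, since the documents give none of these. With equal exits of 25% to 75%, an assumed 25-point difference becomes 18.75 to 6.25 points, and an odds ratio of 3.27 becomes 2.89 to 2.41. The test would rarely register this, so the practical risk is that a non-significant p-value is taken to mean that COVID-19 had no impact. The primary test, the testing hierarchy and the sizing do not change.

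**What to change.** In SAP 4.3.5, add the COVID-19 factor to the existing exemption from the interaction test. Label both of its rows descriptive whatever their size, and note that membership is determined after randomisation. The change carries over to the key secondary endpoints through 4.4.1.2.

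For the impact of COVID-19 in the full ITT population, refer to the planned hybrid analysis. It already imputes Week 24 values that are missing after discontinuation for reasons other than lack of efficacy.

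Optionally, add a variant that multiply imputes only the Week 24 values missing because of COVID-19 and keeps every other primary rule. The model in SAP 5.5 serves for WI-NRS. IGA PN-S needs an adapted model, which the composite key secondary endpoint would also draw on.

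The cost is a short SAP edit and the loss of one interaction p-value per endpoint. The optional variant adds a small amount of programming.

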4.4 SECONDARY ENDPOINT(S) ANALYSIS

The weekly average skin Pain-NRS or Sleep-NRS score at each week, which is defined as the average of non-missing daily scores within the week window of each week (see [Section 5.4](#)), will be used for analyses.

4.4.1 Key/Confirmatory secondary endpoint(s)

4.4.1.1 *Definition of endpoint(s)*

The key secondary endpoint is:

- Proportion of participants with IGA PN-S 0 or 1 score at Week 24.

In addition, for US and US reference countries only, there is another key secondary endpoint:

- Proportion of participants with both an improvement (reduction) in WI-NRS by ≥ 4 from baseline to Week 24 and an IGA PN-S 0 or 1 score at Week 24.

Investigator's global assessment for prurigo nodularis (IGA PN)

The IGA PN is a clinician-reported outcome (ClinRO) that allows clinicians to assess the activity of PN (IGA PN-A) using a 5-point scale from 0 (clear) to 4 (severe); and the stage of the disease (IGA PN-S) using a 5-point scale from 0 (clear) to 4 (severe).

4.4.1.2 *Main analytical approach*

For the key secondary efficacy endpoints, the analysis will be conducted by using CMH test adjusted by documented history of atopy (atopic or non-atopic), stable use of TCS/TCI (yes or no), region, and baseline anti-depressant use (yes or no). The same estimand, ie, intercurrent event strategy and missing data handling method, as the primary endpoint is used.

The same supplementary and subgroup analyses used for the primary endpoint will also be performed for the key secondary efficacy endpoints.

4.4.2 Supportive secondary endpoint(s)

The other secondary endpoints are as follows:

- Proportion of participants with WI-NRS reduction ≥ 4 over time until Week 24.
- Proportion of participants with WI-NRS reduction ≥ 4 at Week 12
- Proportion of participants with WI-NRS reduction ≥ 4 at Week 4
- Proportion of participants with IGA PN-S 0 or 1 score at Week 12
- Proportion of participants with IGA PN-S 0 or 1 score at Week 8
- Proportion of participants with IGA PN-S 0 or 1 score at Week 4
- Proportion of participants with IGA PN-A 0 or 1 score at Week 24
- Proportion of participants with IGA PN-A 0 or 1 score at Week 12
- Proportion of participants with IGA PN-A 0 or 1 score at Week 8
- Proportion of participants with IGA PN-A 0 or 1 score at Week 4
- Time to onset of effect on pruritus as measured by proportion of participants with an improvement (reduction) in WI-NRS by ≥ 4 from baseline during the 24-week treatment period
- Change from baseline in WI-NRS at Week 24
- Change from baseline in WI-NRS at Week 12
- Percent change from baseline in WI-NRS at Week 24
- Percent change from baseline in WI-NRS at Week 12
- Percent change from baseline in WI-NRS at Week 4
- Percent change from baseline in WI-NRS at Week 2
- Percent change from baseline in WI-NRS over time until Week 24.
- Onset of action in change from baseline in WI-NRS (first $p < 0.05$ difference from placebo in the daily WI-NRS that remains significant at subsequent measurements) until Week 12
- Change from baseline in IGA PN-S score at Week 24
- Change from baseline in IGA PN-S score at Week 12
- Change from baseline in IGA PN-S score at Week 8
- Change from baseline in IGA PN-S score at Week 4
- Change from baseline in HRQoL, as measured by Dermatology Life Quality Index (DLQI) to Week 24
- Change from baseline in HRQoL, as measured by Dermatology Life Quality Index (DLQI) to Week 12.

Dermatology life quality index (DLQI)

The DLQI is a PRO developed to measure dermatology-specific HRQoL in adult participants. The instrument comprises 10 items assessing the impact of skin disease on participants' HRQoL over the previous week. The items cover symptoms, leisure activities, work/school or holiday time, personal relationships including intimate, the side effects of treatment, and emotional reactions to having a skin disease. It is a validated questionnaire used in clinical practice and clinical trials. Response scale is a 4-point Likert scale (0 = "not at all" and 3 = "very much") for nine items. The remaining one item about work/studying asks whether work/study has been prevented and then (if "No") to what degree the skin condition has been a problem at work/study; the item is rated on a 3-point Likert scale ("Not at all" to "A lot"). Overall scoring ranges from 0 to 30, with a high score indicative of a poor HRQoL.

Time-to-event secondary efficacy endpoint

Time to first onset of effect on pruritus defined as an improvement (reduction) in WI-NRS by ≥ 4 from baseline during the 24-week treatment period will be analyzed using the Cox proportional hazards model, including treatment, documented history of atopy (atopic or non-atopic), stable use of TCS/TCI (yes or no), region, and baseline anti-depressant use (yes or no). The hazards ratio, its 95% confidence interval and p-value will be reported. Kaplan-Meier curves will be also provided.

For time to first WI-NRS response (WI-NRS by ≥ 4 from baseline), participants who receive the prohibited medications and/or rescue medications (see [Table 5](#)), data prior to start of the medications will be used, but after medication start, the participants' data will not be used and they will be censored at Week 24 (ie, Day 172). For other participants, all available data up to Week 24 (ie, Day 172) including those collected during the off-treatment period will be used. Participants without events will be censored at Day 172 or their last WI-NRS assessment date if discontinued from the study, whichever is earlier.

Secondary efficacy endpoints that measure binary responses

Secondary efficacy endpoints that measure binary responses will be analyzed in the same fashion as the primary endpoint using primary statistical model.

Continuous secondary efficacy endpoints

The primary estimand for continuous secondary efficacy endpoints is defined in [Table 3](#) and will be analyzed using an analysis of covariance (ANCOVA) model with intervention group, documented history of atopy (atopic or non-atopic), stable use of TCS/TCI (yes or no), region (countries combined), baseline antidepressant use (yes or no), and relevant baseline measurement as covariate, with intercurrent event strategy and missing data handling as defined as in [Table 3](#). Specifically, data of participants taking the prohibited medications/procedures and/or rescue medications will be set to missing after the medication usage, and the worst postbaseline value on or before the time of the medication usage will be used to impute missing endpoint value (for participants whose postbaseline values are all missing, the baseline will be used to impute). Participants who discontinue the treatment prematurely are encouraged to follow the planned clinical visits and in those participants who did not take the prohibited medications/procedures

and/or rescue medications, all data collected after treatment discontinuation will be used in the analysis. For these participants, missing data may still happen despite all efforts have been tried to collect the data after treatment discontinuation. For participants who discontinue due to lack of efficacy, all data collected after discontinuation will be used in the analysis, and a WOCF approach will be used to impute missing data if needed. For participants who discontinued not due to lack of efficacy, a multiple imputation (MI) approach will be used to impute missing endpoint value, and this MI method will use all participants excluding participants who have taken the prohibited medications/procedures and/or rescue medications prior to timepoint of endpoint of interest and excluding participants who discontinue due to lack of efficacy.

Each of the imputed complete data will be analyzed by fitting an ANCOVA model as described above. The imputation number will be about 40. Statistical inference obtained from all imputed data will be combined using Rubin's rule. Descriptive statistics including number of participants, mean, standard error, and least squares (LS) mean changes (and standard error) will be provided. In addition, difference of the dupilumab group against placebo in LS means and the corresponding 95% confidence intervals (CI) will be provided along with the p-values.

See [Section 5.5](#) for the sample SAS code for the imputation and the analysis.

For the endpoint of percent change from baseline in WI-NRS at week 24, we will also perform an as-observed plus multiple imputation supplementary analysis as described below.

The data collected after taking all prohibited medications and/or rescue medications will be included in the supplementary analysis to evaluate the robustness of the primary analysis results with respect to the method of handling data while taking the prohibited medications (eg, treatment policy strategy). In addition, for participants discontinuing the study treatment before Week 24, their off-study treatment values measured up to Week 24 will be included in the analysis. For participants having missing data at Week 24 regardless of reason(s), a multiple imputation (MI) approach will be used to impute the missing endpoint value.

